17. ETHICAL CONSIDERATIONS

The study will be conducted in the US under Investigational New Drug (IND) Application 66,827, in compliance with Title 21 of the Code of Federal Regulations (CFR), Part 50 (Protection of Human Subjects), and Part 56 (Institutional Review Board) as well as the principles of the Declaration of Helsinki and its amendments and local country-specific requirements. Institutional Review Boards (IRBs) reviewed and approved the protocol and informed consent. All subjects will be required to give written informed consent prior to participation in the study. This study will be performed in accordance with Good Clinical Practices (GCP) by qualified Investigators.

The study specifically incorporates the following features:

- Randomized study design
- Blinding of subjects and Investigators
- Parallel active control group
- Prospectively stated objectives and analytical plan
- Accepted, pre-specified outcome measures for safety and efficacy
- Investigator meeting (and/or a site initiation visit) prior to study start and a detailed protocol to promote consistency across sites
- Compliance with Good Clinical Practices (GCP), with assessment via regular monitoring.

Quality assurance procedures will be performed at study sites and during data management to assure that safety and efficacy data were adequate and well documented.

17.1 Informed Consent

The Investigator will obtain written informed consent from each subject (or their authorized representative) participating in the study. The form must be signed, witnessed and dated according to local acceptable standards. The informed consent form will contain all the Essential Elements of Informed Consent set forth in 21 CFR Part 50, and the ICH Guideline for Good Clinical Practice, Section 4.8 (see Appendix VIII), and the terms of the Declaration of Helsinki. Copies of the signed document should be given to the subject and filed in the Investigator's study file, as well as the subject's medical record if in conformance with the institution's Standard Operating Procedures.

17.2 Institutional Review Board/Research Ethics Board/Independent Ethics Committee

The study will not be initiated without approval of the appropriate Institutional Review Board/Research Ethics Board/Independent Ethics Committee (IRB/REB/IEC) and will comply with all administrative requirements of the governing body of the institution. This protocol, consent procedures, and any amendments must be approved by the IRB/REB/IEC in compliance with current regulations of the FDA and in accordance with ICH/GCPs. A letter of approval will be sent to the Sponsor prior to initiation of the study and when any subsequent modifications are made. The Sponsor or their authorized representative will keep the IRB/REB/IEC informed, as required by regulations, of the progress of the study as well as of any serious and unexpected adverse events.

17.3 Subject Protection

17.3.1 Subject Privacy

In order to maintain patient confidentiality, all case report forms, study reports and communications relating to the study will identify subjects by initials and assigned subject numbers; subjects should not be identified by name. In accordance with local, national or federal regulations, the Investigator will allow the Sponsor or their designee personnel access

to all pertinent medical records in order to verify the data gathered on the case report forms and to audit the data collection process. Regulatory agencies such as the US Food and Drug Administration (FDA) may also request access to all study records, including source documentation for inspection. No material bearing a patient's name will be kept on file by the Sponsor and patients will be informed of their rights within the ICF.

17.3.2 Rationale for Subject Selection

The selection of subjects for this protocol will not be based on sex, race, or ethnic background.

17.3.3 Participation of Children

Children will not be enrolled in this study.

18. TRIAL ADMINISTRATIVE INFORMATION

18.1 Protocol Amendments

As the trial progresses, any amendments to the study protocol deemed necessary will be communicated to the Investigator by Celsion or its designee. All protocol amendments will undergo the same review and approval process as the original protocol. A protocol amendment may be implemented after it has been approved by the IRB/REB/IEC, unless immediate implementation of the change is necessary for subject safety. In that case, the situation must be documented and reported to the IRB/REB/IEC within 5 working days.

20. APPENDICES

20.1 Appendix I: Child-Pugh Classification of Hepatic Impairment

	Encephalopathy*	Ascites	Bilirubin (mg/dL)	Albumin (g/dL)	INR
Score					
1	Absent	Absent	< 2	> 3.5	< 1.3
2	I / II	Mild / moderate	2 - 3	2.8 - 3.5	1.3 - 1.5
3	III / IV	Severe	> 3	< 2.8	> 1.5

*** Encephalopathy grades:**

Grade 0: normal consciousness personality, neurological exam and electroencephalogram

Grade 1: restless, sleep disturbed, irritable/agitated, impaired handwriting, 5 cps waves

Grade 2: lethargic, time-disoriented, inappropriate, asterixis, ataxia, slow triphasic waves

Grade 3: somnolent, stuporous, place-disoriented, hyperactive reflexes, rigidity, slower waves

Grade 4: unrousable coma, no personality/behavior, decerebrate, slow 2-3 cps activity

Interpretation:

Child Class A: 5 to 6 points

Child Class B: 7 to 9 points

Child Class C: 10 to 15 points

Source:

20.2 Appendix II: New York Heart Association (NYHA) Functional Classification for Heart Failure

A functional and therapeutic classification for prescription of physical activity for cardiac patients.

Class I: patients with no limitation of activities; they suffer no symptoms from ordinary activities.

Class II: patients with slight, mild limitation of activity; they are comfortable with rest or with mild exertion.

Class III: patients with marked limitation of activity; they are comfortable only at rest.

Class IV: patients who should be at complete rest, confined to bed or chair; any physical activity brings on discomfort and symptoms occur at rest.

20.3 Appendix III: Prohibited Medications

The active ingredient compound of ThermoDox (Doxorubicin) is a substrate (major) of CYP2D6, 3A4. Inducers and inhibitors of CYP3A4 may alter the metabolism of ThermoDox. The following CYP3A4 inducers and inhibitors are prohibited from screening through after study treatment. Additionally, medications that could change the pharmacokinetic profile of ThermoDox or modify gastric pH are prohibited. Future updates to the list will be provided to the site as new information becomes available.

Drug Class	Agent	Wash-out ¹
CYP3A4 Inducers		
Antibiotics	all rifamycin class agents (e.g., rifampicin, rifabutin, rifapentine)	14 days
Anticonvulsants	phenytoin, carbamazepine, barbiturates (e.g., phenobarbital)	
Antiretrovirals	efavirenz, nevirapine	
Glucocorticoids (oral)	cortisone (> 50 mg), hydrocortisone (> 40 mg), prednisone (> 10 mg), methylprednisolone (> 8 mg), dexamethasone (> 1.5 mg, except the oral premedication which is part of the protocol) ²	
Other	St. John's Wort, modafinil	
CYP3A4 Inhibitors		
Antibiotics	clarithromycin, erythromycin, troleandomycin	7 days
Antifungals	itraconazole, ketoconazole, fluconazole (> 150 mg daily), voriconazole	
Antiretrovirals, Protease Inhibitors	delavirdine, nelfinavir, amprenavir, ritonavir, indinavir, saquinavir, lopinavir	
Calcium channel blockers	verapamil, diltiazem	
Antidepressants	nefazodone, fluvoxamine	
GI Agents	cimetidine, aprepitant	
Other	grapefruit, grapefruit juice	
	amiodarone	6 months
Miscellaneous		
Antacids ³	Mylanta, Maalox, Tums, Rennies	1 hour before and after dosing
Herbal or dietary supplements	Ginkgo biloba, kava, grape seed, valerian, ginseng, echinacea, evening primrose oil	14 days
Intravenous fat emulsions ⁴		1 day before and after dosing
Lipid complexed drugs	Fentanyl,	1 day before and after dosing
Liposomal drugs	Abelect TM , Ambisome TM , Nyotran TM	1 day before and after dosing

1. At the time of screening, if a subject is receiving any of the above listed medications/substances, the medication or substance must be discontinued (if clinically appropriate) for the period of time specified prior to administration of the first dose of study drug treatment and throughout the period discussed above in order for the subject to be eligible to participate in the study.
2. Glucocorticoid daily doses (oral) \leq 1.5 mg dexamethasone (or equivalent) are allowed. Glucocorticoid conversions are provided in parentheses.
3. Antacids may have an impact on absorption of oral premedication dexamethasone due to a change in stomach pH.
4. Intravenous fat emulsions, with the exception of Propofol, are prohibited.

20.4 Appendix IV: RFA Treatment Procedure

Treating Physician Qualifications

- Must have performed radiofrequency ablation therapy on hepatic tumors in at least 15 patients.
- Must have used RFA device that will be used in protocol to treat hepatic tumors in at least 5 patients.

Ablation Equipment

Only FDA-approved RFA equipment marketed by Covidien, Boston Scientific Corp., and Angiodynamics (RITA) will be used in the protocol; however, each doctor (Principal Investigator or sub-Investigator) performing RFA will be limited to the use of a single manufacturer's device for all treatments for an individual patient.

- Covidien RFA Equipment
 - Monopolar RF ablation generator with automated ablation algorithm (using the current model, which may be replaced with more current models during the course of the study.)
 - Cool-Tip RF ablation needles.
 - Covidien generator Switch Box.
 - Dispersive Electrodes.
- Boston Scientific Corp. RFA Equipment
 - Radiofrequency Generator (using the current model, which may be replaced with more current models during the course of the study.)
 - LeVeen Needle Electrodes.
 - Dispersive Electrodes.
- Angiodynamics (RITA) RFA Equipment
 - Radiofrequency Generator (using the current model, which may be replaced with more current models during the course of the study).
 - StarBurst Electrodes.
 - Dispersive Electrodes.

Ablation Strategy for Individual Tumors

The following are the minimum requirements for ablating tumors of a given size. At least 4 ablation cycles lasting a total of ≥ 45 minutes should be performed. Since all tumors are not perfect spheres, the operator should use the maximum diameter to choose the appropriate ablation strategy. All tumors should be treated with the goal of ablating the tumor as well as a 360° 1.0 cm tumor free margin around each tumor. Updated operational manuals for each RFA device, detailing the specifics of electrode vs. tumor size, should be followed accordingly.

20.5 Appendix V: Adverse Events (AEs) and Criteria for Determining Relationship of AE to Treatment

Criteria for Determining Category of Relationship of Clinical Adverse Events to Treatment

1	Not related	This category applies to those adverse events, which, after careful consideration, are clearly and incontrovertibly due to extraneous causes (disease, environment, etc.).
2	Unlikely (must have two)	In general, this category can be considered applicable to those adverse events, which, after careful medical consideration at the time they are evaluated, are judged to be unrelated to the test drug or/and procedure. An adverse event may be considered unlikely if or when: 
1. It does not follow a reasonable temporal sequence from administration of the test drug or/and procedure.2. It could readily have been produced by the subject's clinical state, environmental or toxic factors, or other modes of therapy administered to the subject.3. It does not follow a known pattern of response to the drug/procedure.4. It does not reappear or worsen when the drug/procedure is re-administered.
3	Possibly (must have two)	This category applies to those adverse events for which, after careful medical consideration at the time they are evaluated, a connection with the test drug or/and procedure administration appears unlikely but cannot be ruled out with certainty. An adverse event may be considered possibly related if or when: 
1. It follows a reasonable temporal sequence from administration of the test drug/procedure.2. It could not readily have been produced by the subject's clinical state, environmental or toxic factors, or other modes of therapy administered to the subject.3. It follows a known pattern of response to the test drug/procedure.
4	Probably (must have three)	This category applies to those adverse events for which, after careful medical consideration at the time they are evaluated, are felt with a high degree of certainty to be related to the test drug or/and procedure. An adverse event may be considered probably related if or when:

1. It follows a reasonable temporal sequence from administration of the test drug/procedure.
2. It could not be reasonably explained by the known characteristics of the subject's clinical state, environmental or toxic factors or other modes of therapy administered to the subject.
It disappears or decreases on cessation or reduction in dose.
3. There are important exceptions when an adverse event does not disappear upon discontinuation of the drug, yet drug-relatedness clearly exists (e.g., bone marrow depression, fixed drug eruptions, tardive dyskinesia).
4. It follows a known pattern of response to the test drug/procedure.

5 Definitely (must have all)
This category applies to those adverse events that the Investigator feels are incontrovertibly related to test drug or/and procedure. An adverse event may be assigned an attribution of definitely related if or when:

1. It follows a reasonable temporal sequence from administration of the test drug/procedure.
2. It could not be reasonably explained by the known characteristics of the subject's clinical state, environmental or toxic factors or other modes of therapy administered to the subject.
3. It disappears or decreases on cessation or reduction in dose with re-exposure to drug. (Note: This is not to be construed as requiring re-exposure of the subject; however, a category of definitely related can only be used when a recurrence is observed.)
4. It follows a known pattern of response to the test drug/procedure.

The Investigators are to record the Outcome to Date using the following four categories:

Outcome		
Code	Descriptor	Definition
1	Recovered	The patient fully recovered from the adverse event with no residual effect observable.
2	Adverse Event Still Present	The adverse event itself is still present and observable.
3	Adverse Event Resolved	The adverse event resolved, but residual effect(s) are still present and observable.
4	Death	Death
5	Unknown	The outcome of the adverse event could not be determined.

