	
Study Drug Infusion: A 50 mg/m² ThermoDox infusion (ThermoDox arm) or dummy infusion of Dextrose 5% Solution or Sodium Chloride 0.9% (Control arm) will be administered IV over 30 minutes.
 
The Sponsor will provide blinded masking materials to maintain the blind and unblinded site representative(s) (i.e. pharmacist) will prepare the materials to cover IV bags and tubing.
 
Radiofrequency Ablation: Only FDA approved RFA devices are permitted for this trial. RFA requiring a standardized dwell time \geq 45 minutes will be initiated 15 minutes (+5 min.) after the start of the study drug infusion with an estimated overall procedure time of less than 3 hours. A standardized Radiofrequency Ablation sRFA treatment for this protocol is defined as the dwell time of \geq 45 minutes measured from the first activation of the RFA probe to produce coagulative necrosis of target tissue through removal of the RFA probe after the final ablation cycle or deployment.. This includes the multiple ablation cycles and repositioning time between cycles for an individual patient. An ablation cycle for this protocol is defined as the single activation of the probe or electrode in order to achieve a local coagulation necrosis in target tissue. The cycle may be completed by achieving a target temperature in the tissue or a target impedance.
 
The goal is to ablate the tumor as well as a 360° 1.0 cm tumor-free margin surrounding the tumor. Tumor uptake of ThermoDox is enhanced with a standardized treatment dwell time of at least 45 minutes (30 minutes with a switchbox). The literature recommends tumors \geq 3 cm should require at least four ablation spheres (if using simple needle electrode) or at least four deployments (if using multiple array LeVeen needle electrode). More ablations may be performed at the discretion of the operator, however the RFA probe dwell time must reach 45 minutes.
 
Pringle maneuver or balloon occlusions are prohibited.

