Study drug will be administered IV over 30 minutes in a blinded fashion.

- Treatment arm subjects will receive a 50 mg/m^2 ThermoDox infusion.

- Control arm subjects will receive a dummy infusion of D5W (250 cc of 5% Dextrose solution) or Saline (250 cc of 0.9% Sodium Chloride).

The Sponsor will provide blinded masking materials to maintain the blind and unblinded site representative(s) (i.e., pharmacist) will prepare the materials to cover IV bags and tubing.

Only US FDA approved RFA devices are permitted for this trial. RFA requiring a standardized dwell time \geq 45 minutes will be initiated at minute 15 (+5 minutes) following the start of the study drug infusion with an estimated overall procedure time of less than 3 hours. An sRFA treatment for this protocol is defined as the dwell time of \geq 45 minutes measured from the first activation of the RFA probe to produce coagulative necrosis of target tissue through removal of the RFA probe after the final ablation cycle or deployment. This includes the multiple ablation cycles and repositioning time between cycles for an individual patient. An ablation cycle for this protocol is defined as the single activation of the probe or electrode in order to achieve a local coagulation necrosis in target tissue. The cycle may be completed by achieving a target temperature in the tissue or a target impedance.

The goal is to reach a $>$ 45 minute dwell time which can be achieved by employing at least four ablation cycles or deployments in order to ablate the tumor as well as a 360° 1.0 cm tumor-free margin surrounding the tumor. Tumor uptake of ThermoDox is enhanced with standardized treatment times of at least 45 minutes (30 minutes with a switchbox). The RFA literature recommends a minimum of 4 ablation cycles to ablate tumors of \geq 3.0 cm together with a 360° 1.0-cm margin (Chen, et al. 2004).

According to literature, tumors \geq 3 cm should require at least four ablation spheres (if using simple needle electrode) or at least four deployments (if using multiple array LeVeen needle electrode). More or fewer ablations may be performed at the discretion of the operator, however the RFA probe dwell time must reach 45 minutes.

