8.3 Use of Radiofrequency Ablation Devices

Only FDA approved RFA devices including the Covidien switchbox and all manufacturer probes for these devices are permitted for this trial. The choice of RFA devices (Angiodynamics, Boston Scientific, or Covidien) will be made at each institution. Physicians (Principal Investigator or sub-Investigator) performing RFA may use more than one RFA device at their local institution. However, the same device must be used for all treatments of an individual patient.

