8.4 Radiofrequency Ablation Procedure

The goal is to reach a ≥ 45 minute dwell time which can be achieved by employing multiple ablation cycles or deployments in order to ablate the tumor as well as a 360° 1.0 cm tumor-free margin surrounding the tumor. Tumor uptake of ThermoDox is enhanced with a standardized RFA treatment dwell time of ≥ 45 minutes (≥ 30 minutes with a switchbox). An sRFA treatment for this protocol is defined as the dwell time of ≥ 45 minutes measured from the first activation of the RFA probe to produce coagulative necrosis of target tissue through removal of the RFA probe after the final ablation cycle or deployment. This includes the multiple ablation cycles and repositioning time between cycles for an individual patient. An ablation cycle for this protocol is defined as the single activation of the probe or electrode in order to achieve a local coagulation necrosis in target tissue. The cycle may be completed by achieving a target temperature in the tissue or a target impedance.

The RFA operator must have experience with performing at least 15 procedures. A minimum of 5 prior cases with the device should be documented.

The standard RFA procedures to achieve adequate dwell time of ≥ 45 minutes must be implemented by the sites.

- a. The tumor should be treated with the goal of reaching a > 45 minute dwell time which can be achieved by employing multiple overlapping ablation cycles (according to literature recommend 4 cycles) thus ablating the tumor as well as a 360° 1.0 cm tumor-free margin around the tumor.
- b. Devices should be operated within manufacturer's instructions.
- c. A percutaneous, laparoscopic, or open surgical approach may be utilized.
- d. The RFA device operator will activate the RFA generator to initiate tumor tissue ablation temperatures at 15 minutes (+5 min.) after the start of the study drug infusion.

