- e. Enhanced local concentration of doxorubicin and tumor uptake from ThermoDox requires at least 45 minutes RFA dwell time. This dwell time is achieved by administering multiple ablation cycles, so 4 ablation spheres (if using a simple needle electrode) or 4 deployments (if using multiple array LeVeen needle electrode) are recommended, but fewer or more may be performed at discretion of the investigator provided the dwell time reaches 45 minutes. The RFA literature recommends a minimum of 4 ablation cycles to ablate tumors of ≥ 3.0 cm together with a 360° 1.0-cm margin (Chen, et al. 2004). More ablations may be performed at the discretion of the operator (Curley, 2001; Dodd, et al. 2001; Chen, et al. 2006).
- f. Investigators are to follow their chosen RFA device's particular guidelines for overlapping ablation procedures (See Appendix IV).
- g. Operators should employ strategies for maximal patient safety based on tumor size and tumor location (Rhim, et al. 2001).
- h. The procedure must be completed within 3 hours from the start of the infusion.
- i. The adequacy of ablation will be monitored by ultrasound, MRI, or CT scan throughout the procedure in accordance to the site's standard of practice.
- j. Pringle maneuver or balloon occlusions are prohibited.

RFA will be performed in accordance with RFA Treatment Procedure described in Appendix IV and manufacturer's instructions provided separately.

In order to avoid potential heating or burns to the skin area in contact with the grounding pads, handling of the skin area around the pads as well as the number of pads used will be determined per the RFA device manual's instructions. Should the temperature of the ground pads rise above 39°C , the RFA treatment will be discontinued until the temperature returns to baseline; additional grounding pads can be employed to avoid skin burns and rising temperature.

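### The required dwell time is 45 minutes for every device, but a bracketed 30-minute switchbox figure and two end points for the dwell clock blur that rule

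*Protocol*

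**What the plan says.** Dwell time is part of the treatment definition. The synopsis and protocol 3.3, 5.1 and 8.4 define sRFA as at least 45 minutes, from first activation of the probe to its removal after the last cycle, with no exception by device. Section 3.3 calls this dwell time the minimum effective dose. The synopsis leaves additional ablations to the operator, "however the RFA probe dwell time must reach 45 minutes", and 5.1 repeats that condition. Item e of 8.4 states: "Enhanced local concentration of doxorubicin and tumor uptake from ThermoDox requires at least 45 minutes RFA dwell time". Appendix IV says "The following are the minimum requirements for ablating tumors of a given size. At least 4 ablation cycles lasting a total of" 45 minutes or more.

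Three sections add a second figure. In the synopsis, uptake is enhanced with a "standardized treatment dwell time of at least 45 minutes (30 minutes with a switchbox"). In 5.1: "Tumor uptake of ThermoDox is enhanced with standardized treatment times of at least 45 minutes (30 minutes with a switchbox"). The first paragraph of 8.4 has the same bracket, there as a minimum of "30 minutes with a switchbox".

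The switchbox is allowed. Section 8.3 says "Only FDA approved RFA devices including the Covidien switchbox and all manufacturer probes for these devices are permitted for this trial", and Appendix IV lists the "Covidien generator Switch Box".

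In the SAP, 6.2.2 defines MRD7 as a dwell time below 45 minutes, and 6.3.2.e re-runs the primary survival analysis without subjects who meet MRD1 to MRD7. Protocol 15.3.2.2.d makes the same exclusion. The SAP never mentions a switchbox.

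Protocol 16.3.1 lists device type, number of cycles, dwell time, probe type, tip length and probe length as intraoperative data. Its note ends the dwell clock when the generator is turned off. SAP 1.2 ends it at probe removal.

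**The concern.** The bracket appears three times, always attached to the standardized time, and no text says what it is for. In 8.4 it directly qualifies the standardized RFA treatment dwell time, the quantity that defines sRFA. An operator using a permitted switchbox could reasonably take it as a device-specific minimum.

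The trial rests on this quantity. Section 3.3 traces the hypothesis to a post hoc finding in the earlier trial for dwell times of at least 45 minutes, and 15.4.1 cites the hazard ratio of 0.63 seen in subjects treated that long. A procedure stopped early because of the bracket would fall short of the treatment under test, and the subject would leave a pre-specified supportive analysis.

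MRD7 is also the only SAP rule that singles out subjects below 45 minutes. Protocol 15.3.2.2.b has a low category for outliers, but the SAP's dwell-time factor is only below 90 versus 90 minutes or more. MRD7 therefore needs a clear threshold and a single clock.

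**Working it through.** **1. The texts side by side**

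| Place | Figure | How it is worded | Switchbox exception |
|---|---|---|---|
| sRFA definition (synopsis, 3.3, 5.1, 8.4) | 45 min or more | definition | none |
| Synopsis and 5.1, operator-discretion sentence | 45 min | must reach | none |
| 8.4 item e | 45 min or more | uptake requires it | none |
| Table 1, footnote 10 | 45 min or more | should achieve | none |
| Appendix IV | 45 min or more | minimum requirement, total over cycles | none |
| Protocol 15.3.2.2.d and SAP MRD7 | 45 min | exclusion threshold | none |
| Synopsis, 5.1, 8.4 first paragraph | 45 min, or 30 with a switchbox | remark on tumor uptake | yes, in brackets |

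Every row worded as a requirement says 45 minutes. The bracket sits in a sentence about uptake. Within 8.4, the first paragraph says uptake is enhanced from 30 minutes with a switchbox, while item e says it requires 45.

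**2. A switchbox procedure with dwell time D, where 30 ≤ D < 45**

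- Bracket: the figure is met.
- sRFA definition, must-reach sentences and 8.4 item e: not met.
- Appendix IV: it does not use the word dwell, but its total of 45 minutes applies to all listed equipment.
- MRD7: major deviation, so the subject is excluded under 6.3.2.e.

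The largest shortfall is 45 − 30 = 15 minutes, and 15/45 is one third.

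**3. The two clocks**

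Let T be the time from first activation to generator-off after the last cycle, and d ≥ 0 the further time until the probe is removed.

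- Dwell time under 16.3.1: T.
- Dwell time under the sRFA definition and SAP 1.2: T + d.

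They disagree on the 45-minute threshold when T < 45 ≤ T + d, that is, when 45 − d ≤ T < 45. The error then runs one way: a subject who meets the sRFA definition is recorded below 45 minutes and meets MRD7. The documents do not give d.

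**4. The primary design**

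Inputs from 15.4.1: hazard ratio 0.67, one-sided 0.025, power 80%, 1:1 allocation, 197 deaths.

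- Schoenfeld: 4 × (1.960 + 0.842)² / (ln 0.67)² = 4 × 7.849 / 0.1604 ≈ 195.8, so 196.
- Freedman: (1.67/0.33)² × 7.849 = 25.61 × 7.849 ≈ 201.0, so 202 after rounding up.
- Power at 197 deaths: Φ(0.4005 × √197 / 2 − 1.960) = Φ(0.85) = 80.2%.

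The plan's 197 is reproduced. No input to it depends on how MRD7 treats the switchbox.

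**The case against.** The strongest reply is that there is only one rule. The 30 minutes is a remark about uptake, and every worded requirement is 45 minutes. In the synopsis and 5.1 a sentence demanding 45 minutes follows shortly after the bracket. The SAP has no exception because the protocol's rule has none. Operators also receive formal training with a manual that is not among the documents. The reading of the rule stands: 45 minutes is the requirement, and protocol and SAP agree on it. What does not follow is that the bracket is harmless. It is repeated three times without explanation, and 8.4 gives two different figures for uptake with a permitted device.

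Three stronger readings are tempting and should not be drawn.

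- A reader might infer that MRD7 wrongly removes switchbox subjects who were treated as the protocol requires. No worded requirement sets 30 minutes, so a procedure of 30 to 44 minutes does not satisfy the protocol.
- A reader might infer a loss of power, either from exclusions or from diluted effect. The documents do not say how many switchbox procedures fell in that range, what effect the drug would have in them, or what power the 6.3.2.e analysis was meant to have. Any figure would come from assumed shares alone.
- A reader might infer that affected subjects cannot be identified. Section 8.3 names the switchbox among the devices and 16.3.1 records device type, so it may be captured. The case report form is not available to settle this.

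**Conclusion.** The point holds as a low-priority ambiguity in the text. The threshold is 45 minutes for all devices; the bracket invites a shortfall of up to 15 minutes, and item e of 8.4 contradicts it. The clock discrepancy stands on its own and does not depend on switchbox use: it affects subjects whose generator-off time is below 45 minutes but whose probe removal is at or after 45.

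The number of subjects affected by either problem is unknown and may be zero. Only MRD7 classification and the supportive analysis that uses it are directly exposed. The conclusion assumes that operators could act on the protocol text and that sites record dwell time as the 16.3.1 note describes; the training manual and the case report form could show otherwise.

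**What to change.** - In the synopsis, 5.1 and 8.4, delete the bracket and state that dwell time, as defined in 8.4, must be at least 45 minutes with every device, including the switchbox. Say the same in Appendix IV, using the term dwell time.
- If the sponsor holds data supporting 30 minutes with a switchbox, write that exception into the sRFA definition and Appendix IV instead, and amend MRD7 to match before unblinding.
- In 16.3.1, end the dwell clock at probe removal.
- Add switchbox use (yes/no) to the intraoperative data in 16.3.1.

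The cost is a few sentences, one data item and, only under the second option, one line in the SAP. The SAP history is dated May 2020 and the protocol planned about 36 months of enrollment. If accrual has ended, protocol edits can no longer guide operators. It would then be enough to state before unblinding that MRD7 applies to switchbox procedures, name the clock it uses, and confirm switchbox use and probe-removal times from source records where these exist.
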